9.2.1.3 Clinical Benefit rate (CBR)

Clinical benefit rate (CBR) will be defined as the proportion of subjects with confirmed CR, PR, marrow CR, or HI. All patients who achieve hematologic CR, PR, marrow CR (with or without HI), or HI without marrow CR per modified IWG response criteria will be considered responders. The response rate and associated 95% confidence interval will be calculated using an exact binomial distribution approach for the ITT, EE and PP populations. In addition, a forest plot of the ORR and corresponding 95% confidence intervals will be provided for each of the risk factors detailed in section 6.3.

9.2.1.4 Cytogenetic Complete Response/Remission rate

Cytogenetic complete response/remission rate will be defined as the proportion of subjects with disappearance of the chromosomal abnormality without appearance of new ones, by cytogenetic assessment in the subset of subjects with abnormal cytogenetics at baseline. The response rate and associated 95% confidence interval will be calculated using an exact binomial distribution approach.

9.2.1.5 Leukemic Transformation rate

Leukemic transformation rate will be determined at landmark time-points of 6, 12, 18, and 24 months and present the transformation rate and corresponding 95% confidence interval.

9.2.2 Time-to-Event Endpoints

9.2.2.1 Duration of Response (DOR)

Duration of Response (DOR) will be analysed for the patients who achieved CR or PR, and for patients who achieved CR, PR, marrow CR or HI separately, and present the median time and associated 95%

confidence interval, analyzed by the Kaplan-Meier method. In addition Kaplan-Meier plots will be provided. Data will be censored as detailed in section 2.3.2. A sensitivity analysis will be performed censoring at the confirmed SCT day, or study drug treatment discontinuation day, if no SCT date can be confirmed. This will be analysed for the ITT population, and will present the median time and associated 95% confidence interval, analyzed by the Kaplan-Meier method. In addition, a Kaplan-Meier plot will be provided. These will be repeated for each of the risk factors detailed in section 6.3.

9.2.2.2 Event Free Survival (EFS)

Event Free Survival (EFS) will be analysed for the EE population and present the median time and associated 95% confidence interval, analyzed by the Kaplan-Meier method. In addition a Kaplan-Meier plot will be provided. These will be repeated for each of the risk factors detailed in section 6.3. Data will be censored as detailed in section 2.3.2.

A sensitivity analysis will be performed censoring at the confirmed SCT day, or study drug treatment discontinuation day, if no SCT date can be confirmed. This will be analysed for the ITT population, and will present the median time and associated 95% confidence interval, analyzed by the Kaplan-Meier method. In addition, a Kaplan-Meier plot will be provided. These will be repeated for each of the risk factors detailed in section 6.3.

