- Leukemic transformation rate: leukemic transformation at landmark time points of 6, 12, 18, and 24 months.
- Event-free survival (EFS), defined as the time from the first day of study drug administration (Day 1) to disease progression, relapse or death from any cause. Subjects who are alive and free from disease progression will be censored at the date of last disease assessment .
- Progression-free survival (PFS): time from the first day of study drug administration (day 1) to progression per IWG criteria, or death on study. Subjects who are alive and free from disease progression will be censored at the date of last disease assessment.
- Overall survival (OS): time from the first day of study drug administration (day 1) to death from any cause on study. Subjects who are alive will be censored at the date of last visit or contact with the investigator.
- Time to Stem Cell Transplant (SCT): time from the first day of study drug administration (day 1) to SCT, for subjects with SCT. If no SCT date can be confirmed, SCT date will be imputed as study drug discontinuation day.

For each of DOR, EFS, PFS and OS, in the sensitivity analyses, subjects with no events who stopped treatment and received SCT will be censored at the SCT day (either confirmed SCT day, or study drug treatment discontinuation day, if no SCT date can be confirmed) even if there were events which occurred after the SCT date.

- For both stages, the rate of treatment discontinuation in the first 3 cycles of therapy due to possibly safety-related reasons will be used as a secondary endpoint to evaluate the safety and tolerability. Progressive disease and transplant are reasons to discontinuation related to efficacy, therefore these events will be excluded from the analysis. All the other reasons for treatment discontinuation will be considered as possibly safety-related, therefore will be included in the analysis as events.

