5.3 Efficacy Evaluable (EE) Population

The Efficacy Evaluable (EE) population for endpoints requiring both bone marrow and peripheral blood assessments is defined as all subjects who

- received at least 2 cycles of therapy and a follow-up bone marrow AND peripheral blood assessments
- or experienced PD prior to completion of 2 cycles of therapy.

The Efficacy Evaluable (EE) population for endpoints requiring either bone marrow or peripheral blood assessment is defined as all subjects who

- received at least 2 cycles of therapy and a follow-up bone marrow OR peripheral blood assessments depending on the corresponding endpoints

or experienced PD prior to completion of 2 cycles of therapy.

The EE population will be used for key efficacy analyses as supportive analyses.

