9.2.2.3 Progression-Free Survival (PFS)

Progression-Free Survival (PFS) will be analysed for the EE population and will present the median time and associated 95% confidence interval, analyzed by the Kaplan-Meier method. In addition a Kaplan-Meier plot will be provided. Data will be censored as detailed in section 2.3.2.

A sensitivity analysis will be performed censoring at the confirmed SCT day, or study drug treatment discontinuation day, if no SCT date can be confirmed. This will be analysed for the ITT population, and will present the median time and associated 95% confidence interval, analyzed by the Kaplan-Meier method. In addition, a Kaplan-Meier plot will be provided. These will be repeated for each of the risk factors detailed in section 6.3.

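### Main EFS and PFS analyses use the efficacy evaluable set, which drops early deaths and leavers without progression, and no ITT run under the same censoring is planned

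*SAP*

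**What the plan says.** SAP 9.2.2.2: "Event Free Survival (EFS) will be analysed for the EE population and present the median time". SAP 9.2.2.3: "Progression-Free Survival (PFS) will be analysed for the EE population and will present the median time". Both apply the censoring of SAP 2.3.2. Each section then adds a second run: "A sensitivity analysis will be performed censoring at the confirmed SCT day", or at the treatment discontinuation day if no transplant date can be confirmed. That second run is on ITT.

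SAP 2.3.2 defines EFS as "time from the first day of study drug administration (Day 1) to disease progression, relapse or death from any cause". PFS also starts on Day 1 and also counts death on study.

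SAP 5.3 gives two versions of EE. One is for subjects who "received at least 2 cycles of therapy and a follow-up bone marrow AND peripheral blood assessments", the other for those who "received at least 2 cycles of therapy and a follow-up bone marrow OR peripheral blood assessments depending on the corresponding endpoints". In both, the alternative way in is "or experienced PD prior to completion of 2 cycles of therapy". On the role of the set, SAP 5.3 says: "The EE population will be used for key efficacy analyses as supportive analyses".

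Protocol 9.2 bases the primary efficacy analysis on ITT (all treated subjects) and gives the forerunner of EE, then called per-protocol, exploratory use only. SAP 13 reports that this set was renamed EE and that a new per-protocol (PP) set was added for a sensitivity analysis. A second SAP section, also numbered 5.3, assigns the primary efficacy analysis to PP.

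**The concern.** Whether a subject is in EE depends on what happens after treatment starts, while the EFS and PFS clocks already run from Day 1. Before 2 cycles are complete, progression brings a subject into EE and counts as an event. A death without progression is also an event by definition, but the subject is removed together with it. Living subjects who stop early without progression are removed too, as are subjects with 2 or more cycles who lack the required follow-up assessment.

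This bears directly on the study's purpose. The rationale in Protocol 1.5 is that early discontinuation may explain the lack of efficacy in MEI-003 and that the lower dose may reduce it. The main EFS and PFS curves would leave out subjects who die or stop early without progression.

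The ITT sensitivity run does not close the gap cleanly. It changes population and censoring together, so a difference from the main run cannot be put down to transplant. In addition, SAP 9.2.2.2 and 9.2.2.3 do not say which EE version applies. SAP 13 does not record the added early-progression route, the blood assessments, the second version, or the use of EE as the main set for these endpoints.

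**Working it through.** The documents give no sample size, event count or expected median for EFS or PFS in this trial, so there is no figure of the plan to reproduce on this point.

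**Step 1. Who is kept before 2 cycles are complete**

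| Subject | Event under SAP 2.3.2 | In EE | In ITT |
|---|---|---|---|
| Progression | yes | yes | yes |
| Death without progression | yes | no | yes |
| Alive, stopped without progression | not yet | no | yes |

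**Step 2. Which runs are planned**

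| Endpoint | Main run | Sensitivity run |
|---|---|---|
| EFS | EE, 2.3.2 censoring | ITT, transplant censoring |
| PFS | EE, 2.3.2 censoring | ITT, transplant censoring |
| OS | ITT, 2.3.2 censoring | ITT, transplant censoring |

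ITT with 2.3.2 censoring is missing for EFS and PFS. The output list in SAP 15 agrees: one overall EFS summary (14.2.5.1) with subgroup versions and one sensitivity table (14.2.5.11); one PFS summary (14.2.6.1) and one sensitivity table (14.2.6.3). The ITT default in SAP 9 does not help, because it gives way where another population is stated.

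**Step 3. Possible size (illustration only)**

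Assumptions: exponential times; ITT median 9 months (MEI-003 EFS, Protocol 1.5); 2 cycles = 56 days.

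- t0 = 56/30.4375 = 1.84 months
- F = 1 − 2^(−1.84/9) = 0.132, the share with an event by t0
- ITT 12-month EFS = 2^(−12/9) = 39.7%

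*(a) Only early non-progression deaths dropped.* Let d be their share of ITT. EE median = 9 × (1 − log2(1 − d)); EE 12-month EFS = 0.397/(1 − d).

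| d | Source | EE median | 12-month EFS |
|---|---|---|---|
| 2% | MEI-004 30-day mortality (Protocol 1.4) | 9.26 | 40.5% |
| 10% | MEI-004 60-day mortality (Protocol 1.4) | 10.37 | 44.1% |
| 13.2% | limit of this model: every early event is such a death | 10.84 | 45.7% |

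The MEI-004 rates are all-cause and from AML, so they are borrowed values and not estimates for this trial.

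*(b) Living leavers dropped.* Let r be the share of those event-free at t0 who are excluded, and k their later hazard relative to those kept. The hazard λ of those kept is set so that the ITT median stays at 9:

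(1 − F) × [(1 − r)e^(−λ(9 − t0)) + r e^(−kλ(9 − t0))] = 0.5

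With D = 1 − d − r(1 − F), EE median = t0 + ln[2(1 − F)(1 − r)/D]/λ.

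Example, r = 0.08, d = 0, k = 2: λ = 0.0724 and D = 0.9306, so the median is 1.84 + ln(2 × 0.868 × 0.92/0.9306)/0.0724 = 9.30.

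| r | d | k = 1 | k = 1.5 | k = 2 |
|---|---|---|---|---|
| 8% | 0 | 8.85 | 9.10 | 9.30 |
| 26% | 0 | 8.41 | 9.19 | 9.85 |
| 8% | 2% | 9.13 | 9.39 | 9.60 |

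The 8% is the MEI-004 discontinuation rate in 2 cycles. The 26% is the MEI-003 pracinostat rate in 3 cycles, which is high for a 2-cycle condition. Both are in Protocol 1.5.

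**Step 4. Scale.** An approximate 95% CI for a 9-month median is 9 × exp(±1.96/√e). With an assumed e = 40 events it is 6.6 to 12.3; with e = 50 it is 6.8 to 11.9. Every median above lies inside both.

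**Step 5. The PP sentence.** Protocol 9.2 names ITT for the primary efficacy analysis. SAP 9 makes ITT the default, with EE and PP in addition. SAP 9.1 reports ORR on all three sets. SAP 13 calls PP a sensitivity set. The PP sentence in SAP 5.3 stands alone against these four.

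**The case against.** The strongest reply is that little is lost in practice. The ITT sensitivity run differs from the missing run only for transplanted subjects, and the protocol says most patients with MDS are not transplant candidates. With no transplants the two would coincide. Early deaths and leavers also appear in ITT overall survival and in the 3-cycle discontinuation rate. This stands, and it limits the harm.

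The text of both sections also repeats the ITT run by the SAP 6.3 factors, one of which is transplant yes or no. Among subjects without transplant, transplant censoring never applies, so for EFS the two no-transplant strata could be compared to show the population effect. But that stratum is itself defined after baseline, it is not an estimate for all treated subjects, the output list names no subgroup sensitivity tables, and the main PFS run is not split this way.

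On the numbers, the net direction is not fixed: only the early-death part must raise the curve. The 8% and 26% are shares of treated subjects, while r is a share of those event-free at t0. Putting them on the treated base changes the medians to 8.83, 9.11 and 9.34 (8%) and 8.29, 9.17 and 9.94 (26%), a move of at most about 0.1 month. The 8% is not stated to exclude progression or death, so combining it with d may count some subjects twice. These points stand, and they are why the figures serve only as illustration.

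Two textual points have partial force. The marrow-or-blood version of EE may be inferred, since progression in Protocol Appendix D can be met on either, but the SAP should say so. And the protocol names no population specifically for EFS or PFS, so the conflict with it is by implication; the conflict within the SAP is direct.

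**Conclusion.** The plan is wrong as written and should be fixed. The SAP uses a set it calls supportive as the main set for two time-to-event endpoints, in a way that removes one kind of endpoint event and keeps another. No ITT estimate under the main censoring is planned, and the sensitivity run changes two things at once.

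The size cannot be known from the documents. Under the stated assumptions the EE median lies between about 8.3 and 10.8 months against 9.0 in ITT. The upward direction is certain only for dropped early deaths; for living leavers it depends on their later hazard. All shifts are within sampling error for the assumed 40 or 50 events. The confidence interval reports sampling error, though, and does not report selection.

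No decision rule changes. EFS and PFS are secondary, SAP 6.5 plans no testing, and ORR is still reported on ITT. The PP sentence is a separate wording conflict with no numerical effect if SAP 9 and 9.1 are followed.

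**What to change.** - In SAP 9.2.2.2 and 9.2.2.3, make ITT (all treated, from Day 1, SAP 2.3.2 censoring) the main analysis, as SAP 9.2.2.4 does for OS.
- Keep EE as supportive for both endpoints and name the version used: marrow and blood, or marrow or blood.
- Keep the transplant-censored ITT run as the sensitivity analysis. It then differs from the main run in censoring only.
- Replace the last sentence of the PP section (the second one numbered 5.3) with one saying that PP serves a sensitivity analysis and ITT is primary.
- In SAP 13, record the changed EE definition and the population used for EFS and PFS.

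The cost is SAP wording, a population flag in the EFS and PFS programs and one supportive EE table for each endpoint. No new data are needed. The ITT curves may look somewhat less favourable than EE if early non-progression deaths dominate, or slightly more favourable if the leavers do as well as those kept.

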9.2.2.3 Progression-Free Survival (PFS)

Progression-Free Survival (PFS) will be analysed for the EE population and will present the median time and associated 95% confidence interval, analyzed by the Kaplan-Meier method. In addition a Kaplan-Meier plot will be provided. Data will be censored as detailed in section 2.3.2.

A sensitivity analysis will be performed censoring at the confirmed SCT day, or study drug treatment discontinuation day, if no SCT date can be confirmed. This will be analysed for the ITT population, and will present the median time and associated 95% confidence interval, analyzed by the Kaplan-Meier method. In addition, a Kaplan-Meier plot will be provided. These will be repeated for each of the risk factors detailed in section 6.3.

9.2.2.4 Overall Survival (OS)

Overall Survival (OS) will be analysed for the ITT population, and will present the median time and associated 95% confidence interval, analyzed by the Kaplan-Meier method. In addition a Kaplan-Meier plot will be provided. These will be repeated for each of the risk factors detailed in section 6.3. Data will be censored as detailed in section 2.3.2.

A sensitivity analysis will be performed censoring at the confirmed SCT day, or study drug treatment discontinuation day, if no SCT date can be confirmed. This will be analysed for the ITT population, and will present the median time and associated 95% confidence interval, analyzed by the Kaplan-Meier method. In addition, a Kaplan-Meier plot will be provided. These will be repeated for each of the risk factors detailed in section 6.3.

10 SAFETY ANALYSIS

Unless stated otherwise, all safety analyses will be performed on the Safety Population.

10.1 Data Monitoring Committee

An independent Data Monitoring Committee (DMC) will be set up for the study; details are provided in the protocol and DMC charter.

10.1 Adverse Events

Treatment-emergent adverse events (TEAEs) will be considered as any event occurring after receiving the first dose of either study drug until 30 days after the last study drug administration.

Treatment emergent adverse events (TEAE) will be classified into a standardized terminology using the Medical Dictionary for Regulatory Activities (MedDRA, version as referenced in the Data Management Plan) System Organ Classifications (SOC) and Preferred Terms (PT), and severity classified according to CTCAE version 4.03. All summaries of the incidence of treatment-emergent adverse events will be provided using the Safety Population for the total group. Although a SOC or PT may be reported more than once for a subject, each subject will only be counted once in the incidence count for that SOC or PT. Summaries of the following types of TEAEs will be provided:

- Overall Summary of Treatment Emergent Adverse Events (TEAEs);
- Summary of TEAEs by MedDRA SOC, PT and Grade (1 or 2, 3 and above);
- Summary of TEAEs related to pracinostat by MedDRA SOC, PT and Grade (1 or 2, 3 and above);
- Summary of TEAEs related to azacitidine by MedDRA SOC, PT and Grade (1 or 2, 3 and above);
- Summary of TEAEs by PT (in descending order)
- Summary of TEAEs leading to discontinuation from the study drug by MedDRA PT, sorted alphabetically by SOC and PT.
- Summary of Treatment Emergent Serious Adverse Events (TESAEs) by MedDRA PT, sorted alphabetically by SOC and PT;
- Summary of TESAEs related to pracinostat by MedDRA SOC, PT and Grade (1 or 2, 3 and above);
- Summary of TESAEs related to azacitidine by MedDRA SOC, PT and Grade (1 or 2, 3 and above);
- Summary of TESAEs by PT (in descending order)
- Summary of TEAEs leading to study treatment interruption
- Summary of TEAEs leading to azacitidine dose reduction

These summaries will present the number and percentage of subjects reporting an adverse event for each classification level. The denominators for calculating the percentages will be based on the number of exposed subjects in the Safety Population (i.e., study drug was administered) in the total group.

All adverse events, serious adverse events and deaths, and adverse events leading to discontinuation from the study will also be provided in data listings by subject.

10.3 Extent of Exposure

The duration of exposure (days) to study drug (pracinostat or azacitidine) will be summarized using descriptive statistics (n, mean, standard deviation, median, minimum, and maximum) in the total group. Duration of exposure will be calculated as the difference between the date of last administration of study drug and the date of first administration of study drug plus 1 day.

The actual dose taken will be determined from the total number of doses taken (dispensed – returned) and the amount of drug per dose. This will be summarized using descriptive statistics for the total group for pracinostat dosing, and by scheduled and overall for azacitidine dosing. The number of cycles will be summarized using descriptive statistics and also in 3-month categories.

Exposure data including date, time, and dose of study drug administration at study site visits, diary dispense/return dates, and study drug dose modifications will be provided in separate data listings by subject. Number (%) of subjects with dose reductions and dose interruptions for both pracinostat and azacitidine will be provided.

10.4 Compliance

Treatment compliance will be assessed for each study drug (pracinostat and azacitidine) at each visit for which study drug can be determined, by comparing the expected number of daily doses and total dose of drug taken with the actual number of daily doses and total dose provided for each. The expected number of daily doses taken will be calculated as the sum of the appropriate number of doses taken and number of doses missed entries from the eCRF. Compliance will be calculated by the formula:

$$\text{Percent Compliance (pracinostat)} = 100 * \frac{\text{Actual \# of daily doses taken}}{\text{Expected \# of daily doses taken}}$$

$$\text{Percent Compliance (azacitidine)} = 100 * \frac{\text{Actual doses administered}}{\text{Expected total dose to be taken} \left(\frac{\text{dose}}{\text{day}} * \text{days} \right)}$$

If the number of doses taken is missing on the eCRF, it will be calculated based on the number of capsules dispensed and returned from the eCRF drug accountability workflow as total number dispensed – total number returned. If the number of doses missed is missing on the eCRF, it will be calculated based on the number of Study Days that have elapsed between the respective visits corresponding to study drug dispense and return.

Treatment compliance will be calculated for each subject/cycle and over all cycle for the Safety Population. Compliance values that are less than 0% will be set to 0%. A summary of treatment compliance will be presented using descriptive statistics for the Safety Population.

Compliance data will be presented within a data listing by subject.

10.5 Prior and Concomitant Medications

Medication usage will be coded using the World Health Organization (WHO) Drug Dictionary. Medication use will be presented for the Safety Population by WHO Drug Anatomical/Therapeutic/Chemical (ATC) category and WHO Drug preferred name. Medication use summaries will be presented for prior medication use (prior to first administration of study drug) and concomitant medication use. Summaries will be provided for the total group. Medications with partial start and/or stop dates, which cannot be definitely categorized as prior or concomitant treatment medications will be considered concomitant.

All summaries will present the number and percentages of subjects using each medication for the total group. The denominators for percentages will be the number of subjects in the analysis population for the total group. A summary of the reason for taking medication will also be provided.

Prior and concomitant medications will be provided in a data listing by subject.

